7.3 LOST TO FOLLOW-UP

Participants classified as lost to follow-up (LTFU) need to meet both of the following criteria:

- a) Failure to respond or reply to 3 documented phone contact attempts followed by
- b) Failure to respond to a certified letter sent to the address provided by the participant.

Only after documentation of these failed attempts to connect with the participant, will they be determined to be LTFU.

8 STUDY ASSESSMENTS AND PROCEDURES

8.1 EFFICACY ASSESSMENTS

This section provides a general description of the procedures and assessments associated with this study.

Informed Consent

Prior to performing any study-related procedures or assessments, the study coordinator discusses the study with the potential participant and obtains signed informed consent. This communication will be

documented. Labs/procedures completed during a routine clinical care appointment that are the same as the study screening labs and/or procedures and completed within the 14 days preceding the screening visit can be used to qualify the participant upon approval by the study PI or designee.

Screening

At the screening visit, participants will screen for the study. Only those participants who meet all eligibility criteria specified in Section 5.1 Inclusion Criteria and Section 5.2 Exclusion Criteria will be enrolled. A unique PID will be assigned during the screening visit.

Participants who are unable to meet protocol-defined eligibility criteria at the Screening Visit (Step 1, Visit 1) may be eligible to re-screen again at the study PI (or designee)'s discretion. In such cases, the same PID will be used. If a screen failure or the failure to move to the next Step is due to the inability to meet one of the laboratory parameters (hematology, chemistry, HIV RNA, or CD4 T cell count), a laboratory retest of the failed criteria may be performed one time only. If the repeat value is within eligibility requirements, the participant can enroll on the study.

Enrollment

Step 1 Visit 1 determines eligibility and enrollment occurs at Visit 2.

Advancement to Step 2

Step 2

Participants enrolled on the study will advance to Step 2 of the protocol based upon the following criteria:

1. A frequency of resting CD4 T cell infection of ≥ 0.3 IUPM as determined by QVOA in Step 1 Visit 2

Note: Participants with prior participation in one of the following UNC protocols in which they had an IUPM measurement ≥ 0.3 , will be able to use this previous measurement for advancement:

- IRB 08-1575 (CID 0819) - Apheresis Procedures to Obtain Leukocytes for Research Studies from HIV Positive Subjects;
- IRB 11-0228 (CID 0807) - NCT01319383;
- IRB 13-3613 (IGHID 1309) - NCT02042248;
- IRB 14-0741 (IGHID 1320) - NCT02208167;
- IRB 15-1626 (IGHID 11424) - NCT02707900;
- IRB 17-0468 (IGHID 11627) - NCT03212989
- IRB 18-0608 (CP-MGD014-01) – NCT 03570918
- IRB 18-0944 (IGHID 1801) -The HIV Reservoir In Women: Implication For HIV Cure Strategies

Note: Participants with these results and measurements from one of the above listed studies, would be able to use these results for advancement to Step 2, but would need to repeat the leukapheresis at Visit 2 to be used as a baseline for this study.

Failure to advance to Step 2 will result in discontinuation from study. Further follow-up is not required as no doses of VRC07-523LS will have been administered.

Medical History

Significant medical history should be obtained during the screening visit. All concurrent medical conditions in the last 30 days and any significant medical conditions (e.g., hospitalizations, surgeries, prior medical history) should be collected. Medical history obtained at Screening will include demographic information (e.g., date of birth, gender, race, and ethnicity, etc.), participant's medical history, and HIV medication history.

Prior and Concomitant Medications

All concomitant medications administered from screening until the end-of-study visit must be recorded in the source documents. Prescription and non-prescription medications taken within 4 weeks prior to screening must be recorded on the source document.

All routine prescription medications, over-the-counter medications, supplements, and study provided medications and investigational products will be entered in the study-specific database, starting at the time of enrollment through the EOS.

Antiretroviral (ART) Medication Assessment

During the study, all modifications to the participant's ART regimen, including any ARV interruptions, dose modifications, formulations modifications, starts, and permanent discontinuations since the last study visit or at the study visit must be recorded.

ART Adherence

ART adherence will be reviewed at every visit. Non-adherence will be defined as missing doses for more than 2 consecutive days or more than 4 cumulative days during the study. Assess any missed doses while on study and discuss with Study PI (or designee). Continuance on study will be contingent on adherence.

Physical Examination

Complete physical examination will include examination of skin, head, eyes, ears, nose, throat, lymph nodes, heart, chest, lungs, abdomen, extremities, and neurologic system according to schedule specified in the SOE in section 1.3.

A directed physical exam will be performed at all clinical visits where a complete physical examination is not performed, according to the SOE in section 1.3. A directed physical examination includes vital signs and addresses any previously identified or new event that the participant experiences since the last study visit or any unresolved signs or symptoms previously experienced. This assessment includes updates to signs and symptoms, and clinical assessment of HIV disease.

Signs and Symptoms Assessments

At entry, all signs and symptoms, regardless of grade, that occurred within the 30 days before entry must be recorded.

Active solicitation of AEs will be done at every study visit. Post-entry signs and symptoms, Grade ≥ 2 , will be recorded. All signs or symptoms, definitely, possibly, or probably related to study interventions, will be recorded, regardless of grade. Additionally, all signs and symptoms that lead to a change in study treatment or change in ART, regardless of grade, must be recorded.

Treatment Emergent Adverse Events

An event that first appears during treatment, which was absent before or which worsens relative to the pre-treatment state.

Vital Signs

Vital signs (weight, body temperature, pulse or heart rate, respiratory rate, and seated blood pressure) will be recorded according to the SOE in section 1.3. Vital sign measurements will be conducted after resting 5 minutes in the sitting position. Height is only required at Step 1, Visit 1.

Repeat vital signs may also be captured as necessary to elucidate the course of any untoward event or AE.

Electrocardiogram

ECG will be performed at screening and should be read per institutional protocol within 72 hours to establish baseline for further evaluation as clinically indicated.

VRC07-523LS Infusions

All study product administrations will be completed per the SOE, section 1.3. Prior to each infusion, temperature (T), blood pressure (BP), heart rate or pulse (P), respiratory rate (RR), and weight will be collected and a targeted PE (based on signs, reported symptoms, or interim medical history) conducted. The participant will be observed for at least 60 minutes following the 1st infusion of VRC07-523LS and at least 30 – 60 minutes after the 2nd VRC07-523LS infusion.

Solicited AE Assessments

For all participants, baseline assessments will be performed before each infusion and assessments for Solicited AEs will be performed after each infusion. All Solicited AEs are graded according to the Division of AIDS Table for Grading the Severity of Adult and Pediatric Adverse Events, Corrected Version 2.1 dated July 2017.

The Solicited AE assessment period is 3 full days following each infusion per the SOE in Section 1.3. Participants are instructed to record symptoms using a daily symptom tool. The study coordinator and the participant will be in contact after the 3-day Solicited AE assessment period, or sooner if indicated. In general, a participant who self-reports any reaction following an infusion that is greater than mild is seen by a clinician within 48 hours after onset, unless the reaction is improving and/or has completely resolved. Clinic study staff will follow new or unresolved Solicited AEs present at day 3 to resolution.

Solicited AE assessments include assessments of systemic and local symptoms, and study product-related lesions.

Assessment of Systemic and Local Symptoms

Systemic symptoms to be assessed as solicited AEs include increased body temperature, chills, malaise and/or fatigue, headache, myalgia, arthralgia, nausea, urticaria, non-exertional dyspnea, non-exertional tachycardia (assessed by CRS staff, not by the participant), generalized pruritus, facial flushing, and unexplained diaphoresis.

Local symptoms include pain or tenderness at the infusion site. The daily maximum severity reached for each symptom during the assessment period is reported.

Body temperature is measured by oral or infrared thermometry and is reported in degrees Celsius. If temperature is measured in Fahrenheit, the conversion to Celsius should be documented in the participant's chart note. A measurement is taken once daily during the assessment period and should be repeated if participant is feeling feverish.

Assessment of Infusion Site

Typical infusion site reactions are erythema/redness and induration/swelling. The maximum horizontal and maximum vertical measurements for all infusion site reactions are recorded.

All infusion/injection site reactions are monitored until resolution. Areas greater than 25 cm² are followed daily; otherwise, the frequency of follow-up is based on clinician judgment.

VRC07-523LS Post Infusion Telephone Follow-Up

Participants will have a telephone interview with a study coordinator 4 -6 days following each infusion to review the solicited AE assessment tool. Any incidents or events identified that could be related to the infusion and are still unresolved at Day 3, will require participants to come into clinic for clinical assessment.

Leukapheresis

Participants will undergo 2 leukapheresis procedures. The baseline leukapheresis will be completed at Visit 2. Participants will advance to Step 2 based on the attainment of an IUPM measurement ≥ 0.3 . The second leukapheresis will occur 5 – 8 weeks after the 2nd series of a VRC-07 infusion followed by VOR dosing.

All protocol-required leukapheresis product will be transported on the day of collection to the [name] Laboratory on the UNC campus.

NOTE: Refer to the UNC Apheresis SOP and Study Specific Lab Manual for procedures specific to this study.

If participants experience a Grade 3 or higher toxicity before completing the screening leukapheresis, they will be discontinued from study, as completing the leukapheresis procedures is a requirement of the study. Participants who experience a Grade 3 or higher toxicity during the leukapheresis will be evaluated on a case-by-case basis to understand the cause of the Grade 3 event. If the clinical situations (i.e., vasovagal response) that lead to the discontinuation of the leukapheresis procedure is determined by the study PI in collaboration with the Apheresis Medical Director to be situational and poses no apparent harm to the participant, the leukapheresis procedure may be repeated. However, if determined by the study PI, Apheresis Medical Director, and/or the Medical Monitor that repeated leukapheresis would be harmful to the participant, then he/she will be terminated from the study. The only exception to this discontinuation policy will be related to elevations in blood pressure (BP). Transiently elevated BPs to Grades 2 and 3 are frequently observed during this procedure, secondary to the BP cuff placement and nervousness of the participant. Elevated BP observed during the leukapheresis procedure will be monitored via Apheresis Lab policies. These will be noted and documented but will not be used to discontinue study participation.

Clinical Laboratory Tests

Blood and urine specimens will be collected according to the SOE in section 1.3. Safety laboratory tests should be performed and reviewed before study drug administration.

Laboratory Assays

Study specific safety and research assays will be collected at the research visits. Safety and clinically relevant labs will be performed at UNC McLendon Laboratories or LabCorp. Research assays will be processed and stored in associated research laboratories. Additional details on collection, processing, storage, and shipping of laboratory samples will be provided in the Study Specific Laboratory Manual.

End of Treatment/End of Study Visit

An End of Study (EOS) visit should occur approximately 2 - 4 weeks after Visit 12 depending on ability to follow the participant and duration and severity of ongoing AEs. An individual participant will be considered to have completed the study if the participant was followed through their last protocol-specified visit/assessment (EOS). Participants who have treatment discontinued due to a DLT or other clinical event will be followed on study until the clinical event is resolved or deemed stable and irreversible. Participants will complete the EOS visit per the SOE (section 1.3) but will be followed as necessary for acceptable resolution of the clinical event.

Participants will be considered not to have completed the study if consent was withdrawn, the study Principal Investigator discontinues the participant from study for severe lack of compliance, or the participant was lost to follow-up.

A list of evaluations to be performed for the EOS visit is provided in the SOE in section 1.3. The EOS Visit should be performed after the participant has met off-study criteria, or has been followed for at least 7 weeks after the last VRC07-523LS dose. Participants experiencing an unresolved AE will be followed until the AE is either resolved or deemed stable and irreversible.

Research Laboratory Assays

The ability of VRC07-523LS infusion in combination with multiple doses of VOR to alter markers of persistent HIV-1 infection in individuals on suppressive ART will be evaluated by measurement of: a) the frequency of resting CD4 T cell infection by QVOA and b) levels of plasma HIV-1 RNA, as measured by low levels of an HIV-1 RNA assay.

Resting CD4 T Cell Infection (RCI)

Lymphocytes are obtained by continuous-flow leukapheresis (samples obtained as per the SOE, section 1.3) and resting CD4 T cells are isolated as previously described (57).

QVOA measurements will be conducted with the leukapheresis samples collected prior to and following combined VOR/VRC07-523LS administration to determine if the frequency of resting CD4 T cell infection, expressed as IUPM, has declined. Since RCI frequency is a definitive measure of the minimum size of the HIV reservoir, a statistically significant decline in response to VRC07-523LS in combination with VOR treatment would be definitive evidence of a reduction in the HIV reservoir.

Plasma for Assays that measure low levels of RNA

Residual low-level viremia will be measured, as evidence suggests that such viremia originates in persistently infected cells, and low-level viremia might be reduced by an augmented antiviral immune response. Plasma for HIV-1 RNA will be obtained as required per the SOE in section 1.3 and stored for batched analyses. Two baseline sample determinations will be obtained during Steps 1 and 2 of the

protocol and 2-4 low level viremia assay measurements after combination therapy with VOR and VRC07-523LS will allow a robust evaluation of changes in plasma levels of cell-free HIV RNA.

Human Leukocyte Antigen (HLA) Typing

HLA testing will be performed at one time point in the study; however, if HLA type is already available in the medical record, it does not need to be repeated. The result will be used for research purposes.

Cytomegalovirus (CMV) IgG Testing

We will perform CMV testing for research purposes only at baseline (Visit 2) and after the 10th dose of VOR in Steps 2 and 3. If positive CMV testing results are available in the medical record, these results will be used for the baseline result. If the previous CMV IgG result in the medical record is negative, the test will be repeated at Visit 2. The 2nd and 3rd tests performed in the research lab will determine whether Vorinostat reactivates CMV enough to detect it in the plasma. The results will not be placed in the participant's medical record.

Epstein-Barr Virus (EBV) Viral Capsid Antigen (VCA) IgG Testing

We will perform EBV testing for research purposes only at baseline (Visit 2) and after the 10th dose of VOR in Step 2 or 3. If positive EBV testing results are available in the medical record, we will use these results for the baseline result. The 2nd and 3rd test performed in the research lab will determine whether Vorinostat reactivates EBV enough to detect it in the plasma. The results will not be placed in the participant's medical record

Vorinostat PK samples

Pharmacokinetic samples will be collected at 3 time points in the study. These will be processed and stored for testing as required.

VRC07-523LS PK samples

Pharmacokinetic samples will be collected at 3 time points: at baseline and after antibody administration at Days 29 (Visit 6) and 89 (Visit 11). These will be processed, stored, and shipped for testing as required.

Anti-Drug Antibody (ADA) Detection Assay

ADA will be measured by using the Meso Scale Discovery (MSD) platform with VRC07-523LS as the target antigen. Anti-VRC07-523LS antibody assays will be performed on serum samples collected at baseline and after antibody administration at Days 29 (Visit 6) and 89 (Visit 11). Serum will be stored at other visits per the SOE. Additional ADA testing may be performed on participants if indicated.

Virology and Viral Sequence Analysis

Samples will be collected per the SOE. Samples will be processed, stored, and analyzed as required.

Cell associated RNA Assay (caRNA)

Samples collected to isolate resting CD4 T cells and run the caRNA assay to have an additional baseline point. It will provide an idea of the baseline variation in caRNA of a given participant. This is important in trying to measure a change in caRNA after the intervention.

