9.4.3 ANALYSIS OF THE OTHER ENDPOINT(S)

Other Activity Endpoints:

- **Change in the frequency of HIV infection per million resting CD4⁺T cells (RCI) from baseline to after treatment with VRC07-523LS and VOR**

We will analyze pre-VOR/VRC07-523LS and post- VOR/VRC07-523LS frequency of HIV infection per million resting CD4⁺T cells using a non-parametric 2-sided sign test (supplemented by longitudinal regression modeling to estimate the magnitude of changes) to determine whether or not a significant decrease of IUPM is observed. With 12 participants, there will be 80% power to reject H₀ (change expected with ART alone) in favor of H_A (greater change than expected with ART) if the true probability of observing a decrease in IUPM in a participant after VOR/VRC07-523LS is 0.93.

This is based on a 2-sided alpha = 0.05 and the assumption that observed HIV infection frequency would decrease with probability 0.54 on ART alone after 6 months without intervention, based on the decay of IUPM seen on ART alone [Crooks 2015, Siliciano 2003].

In addition to summarizing the number and proportion of participants who show decrease in IUPM after VOR/VRC07-523LS, we will describe the magnitude of the changes in decrease in IUPM after VOR/VRC07-523LS via the median fold-change and corresponding 95% confidence interval. We will also summarize the proportion of participants with >6-fold decreases; this magnitude change is rarely seen in participants on stable ART [9].

Other Endpoints: Activity

- **HIV-1 RNA by low level viremia assay measurement at baseline and after treatment with VRC07-523LS and VOR**

The virologic analysis will include estimation of the low level viremia levels at pre-treatment (screening and entry) and separately at post-treatment. We assume that the probability would be 0.10 (10%) for a baseline (pre-entry, entry) detectable low level viremia ≥ 1 copy. The assumption that 10% of participants with a quantifiable low level viremia at screening will have low level viremia assay below the limit of detection at a pre-treatment measure is an estimate based on data from A5244 in which 6 of 50 (12%) enrolled participants had undetectable low

level of viremia at pre-entry and 5 of 51 (10%) at entry after having a screening low level of viremia ≥ 1 copy (59).

Other Exploratory Analyses:

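### For participants who advance on the Visit 2 QVOA, the qualifying value is also the baseline, so IUPM will tend to fall without any drug effect; Section 9.4.3 makes no stated allowance for this, and the fold-change is affected most

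*Combined protocol and SAP*

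**What the plan says.** The Synopsis (1.1) requires a baseline QVOA of at least 0.3 IUPM to advance, and gives 0.3 as the assay's lower limit of detection. Section 8.1 (Advancement to Step 2) repeats the threshold, "as determined by QVOA in Step 1 Visit 2", and the Leukapheresis paragraph of 8.1 makes the Visit 2 collection the baseline.

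Section 8.1 also has an exception. A participant with an IUPM of at least 0.3 in one of several listed UNC protocols may advance on that earlier result, but must "repeat the leukapheresis at Visit 2 to be used as a baseline for this study". There are thus two routes into Step 2. In one, the qualifying value is the baseline. In the other, the baseline is a fresh measurement that played no part in selection.

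Section 9.4.3 compares IUPM before and after treatment "using a non-parametric 2-sided sign test". It states: "With 12 participants, there will be 80% power to reject" the null if the true probability of a decrease is 0.93, at "2-sided alpha = 0.05". The null assumes that "observed HIV infection frequency would decrease with probability 0.54 on ART alone after 6 months without intervention". The size of the change is summarised by the median fold-change with a 95% confidence interval and by the proportion with more than 6-fold decreases. There is no control arm (4.2). Section 8.1 (Resting CD4 T Cell Infection) says that a statistically significant decline "would be definitive evidence of a reduction in the HIV reservoir".

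**The concern.** A QVOA result is the true frequency plus assay error. When entry depends on the result being at or above 0.3, people measured low by chance are excluded and people measured high by chance are retained. The second measurement is not selected, so on average it falls back towards the true value. For Visit 2 qualifiers this regression to the mean looks like a treatment effect.

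Without a control arm, the sign test has only the assumed 0.54 to be judged against, and the median fold-change has no stated reference value at all. If selection alone raises the proportion of decreases and enlarges the fold-change, part of any apparent activity could be an artefact of the entry rule. The documents do not say whether the cohorts behind 0.54 were selected on a measurable baseline in the same way.

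**Working it through.** **1. The plan's own figure.** With n = 12 and null 0.54, the upper tail is P(X ≥ 10) = 0.0363 and P(X ≥ 11) = 0.0069. Holding the upper tail at 0.025 gives rejection at 11 or more of 12. Power at 0.93 is P(X ≥ 11) = 0.797, which reproduces the stated 80%.

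**2. Assay error implied by the plan.** Section 2.1 gives a reservoir half-life of 3.6 years (43.2 months). Decay over 6 months is 0.301 × 6/43.2 = 0.0418 log10. If paired differences are Gaussian with independent errors, a probability of decrease of 0.54 means 0.0418/SD = z(0.54) = 0.1004. So SD = 0.416 log10 for a difference, and 0.416/√2 = 0.294 per assay. Rounding of 0.54 (0.535 to 0.545) moves the paired SD between 0.48 and 0.37.

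**3. Effect of selection among Visit 2 qualifiers.** The documents give no IUPM distribution. I assumed median true IUPM of 0.5, 1 or 2 and between-person SD of 0.3 to 0.6 log10, simulated pairs with decay only, and kept those with a baseline of at least 0.3. The schedule puts the interval from Visit 2 to the second leukapheresis between 0 + 60 + 35 = 95 and 42 + 60 + 56 = 158 days. The midpoint is about 4.2 months. I used that and the plan's 6 months.

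| Interval | Median true IUPM | P(decrease), no drug effect | Apparent fold decrease | Fold decrease from decay alone | Upper tail of 11/12 if all 12 qualify on Visit 2 |
|---|---|---|---|---|---|
| 4.2 months | 0.5 | 0.60–0.63 | 1.28–1.35 | 1.07 | 2.1–3.1% |
| 4.2 months | 1 | 0.57–0.58 | 1.18–1.20 | 1.07 | 1.1–1.3% |
| 4.2 months | 2 | 0.54–0.55 | 1.10–1.14 | 1.07 | 0.7–0.9% |
| 6 months | 0.5 | 0.62–0.64 | 1.32–1.39 | 1.10 | 2.5–3.8% |
| 6 months | 1 | 0.58–0.59 | 1.21–1.23 | 1.10 | 1.4–1.6% |
| 6 months | 2 | 0.55–0.57 | 1.13–1.17 | 1.10 | 0.8–1.1% |

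Ranges within a row are over the between-person SD. Fold decreases are geometric means; the medians are within 0.01 of them. Without selection, P(decrease) is 0.53 at 4.2 months and 0.54 at 6 months. Outside these assumptions the effect can be larger: a median at the threshold itself (0.3) gives up to 0.70 at the same assay SD.

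**4. Consequence for the sign test.** The 11/12 rule keeps its upper tail at or below 2.5% up to a null of 0.615 (P(X ≥ 11) = 0.0249). Above that, 12/12 is needed, and power at 0.93 falls to 0.93^12 = 41.9%.

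**5. Mixed routes.** Take the unfavourable 0.64 for Visit 2 qualifiers and 0.54 for historical qualifiers. The upper tail of 11/12 is 3.7% with 12 Visit 2 qualifiers, 2.4% with 9, 2.1% with 8 and 1.6% with 6.

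**6. More than 6-fold decreases.** With an assay SD of 0.294 and a 6-month interval, the no-effect proportion is 3.8% without selection and about 4 to 5% with it. This summary is little affected.

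**The case against.** A reader might infer that every baseline in the trial is selected. The documents do not support that. Historical qualifiers have a baseline that was not used for selection, and Section 5.5 recruits from the site's own research databases, so this route may be common. A historical qualifier whose Visit 2 value is below 0.3 cannot show a measurable decrease. If such pairs count as no decrease, the null in that route is 0.45 to 0.54 (median true IUPM 0.3 to 2), which partly offsets the bias in the other.

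A reader might also infer that 0.54 describes unselected pairs. Section 9.4.3 says only that it rests on decay of IUPM on ART alone, from two cited studies. Whether those required a measurable baseline is not stated, so the criticism is that no allowance is stated, not that the figure is known to be wrong.

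A third tempting reading is that the sign test is seriously anti-conservative. One exact two-sided convention does reject at 10/12 (0.0363 + 0.0095 = 0.046), and that rule would fare worse. But its power at 0.93 is 95.3%, so it is not the rule behind the stated 80%. Under 11/12 the discreteness of the test absorbs most of the shift.

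Finally, the endpoint is exploratory. Section 9.4.3 stresses estimation, urges caution, and limits analysis to descriptive and within-participant summaries if the study stops at 12. All of this stands and lowers the stakes for the test. It does not protect the median fold-change, which is itself a descriptive summary and gains nothing from discreteness.

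**Conclusion.** The point holds for participants who advance on the Visit 2 QVOA. In that route selection raises the no-effect probability of a decrease to about 0.54 to 0.64, and the apparent fold decrease to 1.10 to 1.39 against 1.07 to 1.10 from decay alone. The direction is certain. The size rests on the back-solved assay SD of about 0.29 log10, Gaussian independent errors, and the assumed IUPM distribution; it is small when most participants are well above 0.3.

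For the sign test, the upper tail of 11/12 would be 0.7 to 3.8% if all 12 qualified on Visit 2. It passes 2.5% only if the overall null exceeds about 0.615, which under these assumptions needs a median near 0.5 and nearly all participants in this route. The effect on the whole sample cannot be fixed, because the mix of routes is not stated. The main consequence is for the fold-change, and for the claim of definitive evidence, which an uncontrolled exploratory comparison cannot carry.

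**What to change.** - **Section 9.4.3, reporting.** Give the number of decreases and the median fold-change separately by qualifying route (Visit 2 or historical IUPM). State how values below 0.3 are counted, since the historical route can produce them at baseline.
- **Section 9.4.3, reference values.** For Visit 2 qualifiers, compare both results with those expected on ART alone given a baseline of at least 0.3. Obtain these by simulation over a stated range of assay SD and IUPM distribution, at the planned interval.
- **Section 9.4.3, critical count.** Keep 11/12 while the resulting null is at or below 0.615. Above that, state 12/12 and restate the power (41.9% at 0.93).
- **Section 8.1, Resting CD4 T Cell Infection.** Replace the definitive-evidence statement with wording suited to an uncontrolled, exploratory before-and-after comparison.

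The cost is a short simulation, some SAP text and possibly a lower stated power. No new data or procedures are needed.
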